### 3.9 Efficacy analysis

Efficacy analysis will be performed on the m-ITT, AT, and PPS datasets. The m-ITT dataset will be the primary analysis set for efficacy evaluation, while the AT and PPS datasets will serve as sensitivity analyses.

#### 3.9.1 Primary efficacy endpoint

The primary efficacy endpoint, "the proportion of patients with mRS  $\leq 2$  at 90 days after onset," will be statistically described by treatment group. The 95% confidence intervals (CIs) will be calculated using the exact Clopper-Pearson method. Additionally, a bar chart will be used to display the distribution of mRS scores.

When using a superiority hypothesis test, the specific statistical hypotheses are as follows:

Null hypothesis  $H_0: p_T - p_C \leq 0$

Alternative hypothesis  $H_1: p_T - p_C > 0$

$\alpha = 0.025$  (one side)

If the hypothesis is adjusted to a non-inferiority hypothesis after the interim analysis, the specific statistical hypotheses are as follows:

Null hypothesis  $H_0: p_T - p_C \leq -15\%$

Alternative hypothesis  $H_1: p_T - p_C > -15\%$

$\alpha = 0.025$  (one side)

Here,  $p_T$  represent the proportions of patients with mRS  $\leq 2$  in the IVT followed by EVT and EVT alone groups, respectively.

A log-binomial model will be used, assuming the primary endpoint follows a binomial distribution. A log-link function will be applied, with covariates including age, pre-stroke mRS, time from onset to randomization, stroke severity (NIHSS score), and collateral circulation. Adjusted and unadjusted risk difference (RD) and risk ratio (RR) with their 95% confidence intervals will be reported.

For superiority, if the lower bound of the 95% CI of the adjusted RD  $> 0$ , superiority is established.

For non-inferiority, if the lower bound of the 95% CI of the adjusted RD  $> -15\%$ , non-inferiority is established.

Additionally, Chi-square tests (expected cell count  $\geq 5$ ), continuity-corrected chi-square tests (1 expected cell count between 1 and 5), or Fisher's exact test ( $\geq 1$  expected cell count  $< 5$  or any expected cell count  $< 1$ ) will also be used for group comparisons, and P-values will be reported.

The mRS score used in the primary analysis will be based on centralized assessments. If centralized assessments are missing for certain subjects, local investigator assessments will be used by default. Sensitivity analyses will also use local assessments to evaluate the robustness of the results.

A list of all primary efficacy endpoint data for all visits (m-ITT, AT, PPS sets) will be provided.

#### 3.9.2 Secondary efficacy endpoints

The secondary efficacy endpoints are as following:

- (1) Proportions of patients with mRS = 0 or 1 at 90 days after stroke onset.
- (2) Proportions of patients with mRS = 0–3 at 90 days after stroke onset.
- (3) mRS score at 90 days after stroke onset.

(4) NIHSS score at 18–24 hours after procedure, 24–74 hours after procedure, and 5–7 days after stroke onset and their changes from baseline.

(5) Proportions of patients with a NIHSS score = 0 or 1, a NIHSS score = 0–2, a NIHSS score improvement  $\geq 4$  points, and a NIHSS score improvement  $\geq 8$  points at 18–24 hours after procedure, 24–74 hours after procedure, and 5–7 days after stroke onset.

(6) Glasgow coma scale score (GCS) at 18–24 hours after procedure, 24–74 hours after procedure, and 5–7 days after stroke onset and their changes from baseline.

(7) Barthel Index score (BI) and proportions of patients with BI = 95–100 at 30 and 90 days after stroke onset.

(8) EQ-5D-5L score at 90 days after stroke onset.

(9) eTICI score and successful reperfusion rates before and after EVT.

(10) mAOL score and recanalization rates at 24–72 hours after procedure.

(11) PC-ASPECTS score at 24–72 hours after procedure and 5–7 days after stroke onset.

(12) Lesion volume based on quantitative imaging detection at 24–72 hours after procedure and 5–7 days after stroke onset.

For categorical endpoints (1, 2, 5, 7, 9, and 10), proportions will be calculated with 95% CI using the exact Clopper-Pearson method. Group comparisons will use chi-square tests, continuity-corrected chi-square tests, or Fisher's exact test, as appropriate, and P-values will be reported. RD and RR with 95% CIs will also be calculated. Both unadjusted and adjusted results will be reported. Covariates include age, pre-stroke mRS, time from onset to randomization, NIHSS score, and collateral circulation.

For continuous endpoints (4, 6, 7, 8, 11, and 12), group comparisons will use independent samples t-tests (if normality and homogeneity of variance are satisfied) or Wilcoxon rank-sum tests (if not). Mean differences with 95% CIs will also be calculated. Both unadjusted and adjusted results will be reported. Covariates include age, pre-stroke mRS, time from onset to randomization, NIHSS score, and collateral circulation.

For endpoint (3), shift analysis will be performed using ordinal logistic regression to calculate the common odds ratio and its 95% CI. Both unadjusted and adjusted results will be reported. Covariates include age, pre-stroke mRS, time from onset to randomization, NIHSS score, and collateral circulation.

A list of secondary efficacy endpoints for all visits (m-ITT, AT, PPS sets) will be provided.

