#### 3.2.2 Reporting standards for analysis results

The ITT, m-ITT, and PPS datasets will be analyzed according to the randomized treatment groups, while the AT and SS datasets will be analyzed based on the actual interventions received. Issues related to cases or data handling not explicitly described in the clinical trial protocol will be resolved following case discussions.

Continuous variables will be described using the mean, standard deviation, median, quartiles, minimum, and maximum values. Categorical and ordinal data will be summarized using frequencies and percentages. Statistical measures and the number of decimal places will be reported as outlined in the table below:

Name	Description	Decimal Places (dp)
Quantitative Data		
N	Number of subjects without missing results	0 dp
Mean	Arithmetic mean	Raw data decimal places + 1 dp

SD	Standard deviation	Raw data decimal places + 1 dp
Median	Median value	Raw data decimal places
Q1	25th percentile (first quartile)	Raw data decimal places
Q3	75th percentile (third quartile)	Raw data decimal places
Min	Minimum value	Raw data decimal places
Max	Maximum value	Raw data decimal places
Missing	Number of missing cases	0 dp; if the percentage frequency is less than 0.1%, the percentage will be displayed to the first non-zero digit. For example, if the percentage is "0.000523%", it will be displayed as "0.0005%" instead of "0.0%".
Qualitative (Categorical and Ordinal) data		
n	Number of subjects with a specific evaluation indicator value	0 dp
%	Percentage (0-100%)	1 dp
Statistical measures		
95% CI	95% confidence interval	Raw data decimal places + 2 dp

The comparison of baseline characteristics between the two groups will be conducted using appropriate statistical methods according to the type of data. For quantitative variables, an independent samples t-test will be used if normality and homogeneity of variance are satisfied; otherwise, the Wilcoxon rank-sum test will be applied. For categorical data, a chi-square test will be used if all expected cell counts are  $\geq 5$ , a continuity-corrected chi-square test will be used if one expected cell count is between 1 and 5, and Fisher's exact test will be applied if more than one expected cell count is between 1 and 5, or if any expected cell count is  $< 1$ . For ordinal data, the Wilcoxon rank-sum test will be used without adjusting for center effects, while the Cochran-Mantel-Haenszel (CMH) test will be applied if adjustments for center effects are needed.

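### SAP 3.9.2 gives the ordered eTICI and mAOL scores no efficacy test that uses their order; assigning the ordinal model already planned for the mRS would be a cheap improvement

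*SAP*

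**What the plan says.** SAP 3.9.2 lists endpoint 9 as "eTICI score and successful reperfusion rates before and after EVT" and endpoint 10 as "mAOL score and recanalization rates at 24–72 hours after procedure". Each names a score and a rate.

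It then assigns methods by endpoint number:

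- **Categorical list (1, 2, 5, 7, 9, 10).** "For categorical endpoints (1, 2, 5, 7, 9, and 10), proportions will be calculated with 95% CI using the exact Clopper-Pearson method". The tests follow: "Group comparisons will use chi-square tests, continuity-corrected chi-square tests, or Fisher's exact test, as appropriate, and P-values will be reported". RD and RR are added, unadjusted and adjusted.
- **Continuous list.** "For continuous endpoints (4, 6, 7, 8, 11, and 12), group comparisons will use independent samples t-tests", or Wilcoxon rank-sum tests if the t-test assumptions fail. Endpoint 7 (Barthel Index score and the proportion at 95–100) is here as well as in the categorical list. Endpoints 9 and 10 are not.
- **Endpoint 3 (mRS score).** "For endpoint (3), shift analysis will be performed using ordinal logistic regression to calculate the common odds ratio and its 95% CI".

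SAP 3.2.2 has a rule for ordered data, "For ordinal data, the Wilcoxon rank-sum test will be used without adjusting for center effects", but it stands in the paragraph on comparing baseline characteristics. SAP 3.8 says only that eTICI grading will be described by group. Protocol 10.2 names an ordinal model only for the mRS shift.

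Protocol Appendix 6 gives eTICI the ordered working grades 0, 1, 2a, 2b, 2c and 3. Appendix 7 gives mAOL grades 0 to 3. Protocol 5.3 defines successful reperfusion as eTICI 2b–3. No section states which mAOL grades count as recanalization.

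**The concern.** Protocol section 2 names reperfusion (eTICI) and recanalization (mAOL) among the secondary objectives. They also bear on the rationale in Protocol section 1, that combined treatment joins fast thrombolysis with the high recanalization of EVT. A reader will want to know whether IVT moved patients up these scales.

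As the lists stand, no efficacy method for these two scores uses the order of the grades. A general chi-square or Fisher test treats a move from 2b to 3 like any other difference between categories and spends a degree of freedom on each extra grade. RD and RR have no meaning for a score with four or six grades. If the paragraph was meant for the rates only, the score comparisons are not prespecified, and a method would have to be chosen later in an open-label trial.

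**Working it through.** **1. The plan's own figure.** The only power calculation is for the primary endpoint (SAP 1.5): 42.03% against 26.14%, one-sided 0.025, 80% power, 1:1.

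n per arm = (1.960 + 0.842)² × [0.4203 × 0.5797 + 0.2614 × 0.7386] / 0.1589² = 7.849 × 0.4367 / 0.02525 = 135.8, so 136. With 20% dropout, 272 / 0.8 = 340, or 170 per arm. Both figures reproduce. No power is stated for eTICI or mAOL.

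**2. Cost of ignoring order, without assuming a grade distribution.** A 1-df test at two-sided 0.05 with 80% power has noncentrality (1.960 + 0.842)² = 7.85. An unordered two-arm chi-square has (grades − 1) degrees of freedom. At the same noncentrality:

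- mAOL, 4 grades, 3 df: 64% power. Regaining 80% needs noncentrality 10.90, and 10.90 / 7.85 = 1.39, so about 39% more patients.
- eTICI, 6 grades, 5 df: 56% power. Regaining 80% needs 12.83, and 12.83 / 7.85 = 1.63, so about 63% more patients.

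This holds when the effect is a shift that an ordinal 1-df test fully captures.

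**3. Simulation under a proportional-odds shift.** Assumed lower-arm mixes: eTICI 5/3/7/30/20/35% over the six grades; mAOL 8/4/18/70% over grades 0–3. The common odds ratio of 1.8 is also assumed. Each cumulative odds of a worse grade is divided by 1.8. For example, 15% below eTICI 2b has odds 0.15 / 0.85 = 0.1765. Then 0.1765 / 1.8 = 0.0980, or 8.9%, so the 2b–3 rate goes from 85% to about 91%. mAOL grade 3 goes from 70% (odds 2.333) to odds 4.2, or 80.8%. Tests are at two-sided 0.05.

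| Score | n per arm | Unordered chi-square | Wilcoxon |
|---|---|---|---|
| eTICI | 136 | 49% | 74% |
| eTICI | 170 | 61% | 86% |
| mAOL | 136 | 39% | 57% |
| mAOL | 170 | 47% | 63% |

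A repeat with 10,000 trials per setting agreed to within about two points. With no effect, both tests rejected in about 5% of trials.

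**4. Other assumed mixes** (170 per arm).

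- eTICI with 75–92% at 2b–3, odds ratio 1.75: chi-square 50–57%, Wilcoxon 76–82%.
- mAOL with 65–75% at grade 3, odds ratio 1.75: chi-square 38–49%, Wilcoxon 55–66%.
- eTICI before EVT, assumed 80/10/5/3/1/1%, odds ratio 2.0: chi-square 55%, Wilcoxon 81%.

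**5. What the binary rates recover** (170 per arm, odds ratio 1.8, mixes of step 3).

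- eTICI 2b–3: about 41–43%.
- mAOL cut at grade 3: about 63–64%, level with Wilcoxon.
- mAOL cut at grades 2–3: about 36%.

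**6. Benefit at one cut only.** Let eTICI 2b–3 rise from 85% to 95%, with 2c and 3 unchanged. At 170 per arm the binary test has about 89%, the unordered chi-square 72–74% and Wilcoxon about 12%. Here the order-based test is the poor one.

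**The case against.** A reader might infer that the SAP has chosen a chi-square over the eTICI and mAOL grades and so gives away power. The text does not establish that. Clopper-Pearson intervals, RD and RR are tools for binary outcomes. Endpoints 1, 2 and 5 and the proportion in endpoint 7 are binary, and endpoints 9 and 10 each name a rate that fits. The more coherent reading is that the paragraph covers the rates and the scores were left without a method. On that reading the planned comparison is the 1-df rate test, and the power figures for a grade-wise chi-square do not describe the plan.

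A reader might also infer that an ordinal test must be stronger. The documents give no expected distribution or pattern of benefit. Step 6 reverses the ranking, and step 5 shows that a grade-3 mAOL rate would lose nothing under the assumed shift.

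Finally, the Wilcoxon rule in SAP 3.2.2 falls under the general principles and may show the intended method. The table shells named in SAP section 4, which are not available here, may settle the matter.

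These points limit the claim but leave a gap. The SAP used the double listing for the Barthel Index and not for eTICI or mAOL, and the ordinal rule sits in a baseline paragraph. On either reading, no efficacy test that uses grade order is assigned to these scores.

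**Conclusion.** The point holds as a gap in specification. Endpoints 9 and 10 are listed under categorical methods only. Literally, their ordered scores are tested without regard to order; on the charitable reading, they have no efficacy test.

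The size is conditional. With the assumed mixes and a uniform odds ratio of 1.8, at 136 to 170 per arm, an ordinal or rank test gains about 25 points over an unordered chi-square for eTICI (74 − 49; 86 − 61). For mAOL it gains about 16 to 18 points (63 − 47; 57 − 39). The gain shrinks or reverses when the benefit is concentrated at one cut, so the binary rates should stay.

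The documents do not support a claim that the trial will miss a reperfusion effect. These are secondary endpoints with no stated power, and the primary analysis is untouched. This is a cheap improvement.

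**What to change.** In SAP 3.9.2:

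1. Assign the eTICI score (before and after EVT) and the mAOL score to the ordinal logistic model already used for endpoint 3: common odds ratio with 95% CI, unadjusted and adjusted for the same covariates.
2. Add a check of proportional odds, with the Wilcoxon rank-sum test as the stated fallback.
3. State that chi-square or Fisher tests, Clopper-Pearson intervals, RD and RR apply to the binary rates: eTICI 2b–3, and recanalization with its mAOL cut written down.

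The cost is a sentence or two in the SAP and matching table shells, with no new data or patients. The one downside is reliance on proportional odds, which the retained rate tests cover. The change should be dated before any unblinded comparison of these endpoints.

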8.1.4 Additional study parameters

Baseline parameters to be recorded include demographic data such as age, sex, ethnicity, and body mass index, as well as clinical histories, including prior stroke, comorbidities (e.g., hypertension, diabetes, atrial fibrillation, and myocardial infarction), smoking, alcohol consumption, prior medications (e.g., antiplatelets and anticoagulants), and vital signs (e.g., blood pressure, temperature, pulse, and respiration rate). Neurological assessments include pre-stroke mRS, NIHSS, and GCS scores. Clinical laboratory tests include INR, APTT, platelet count, and blood glucose levels. Imaging results will include PC-ASPECTS, PMI (Pons-midbrain index; **Appendix 13**), PC-CS (Posterior circulation collateral score; **Appendix 14**), and BATMAN (Basilar artery on CT angiography; **Appendix 15**) scores.

We will document the actual dose, type, route, and administration time of IVT medications. Additionally, we will record the time intervals from symptom onset to emergency department arrival, CT/MR/DSA imaging, randomization, IVT initiation, EVT procedure initiation, reperfusion, and EVT procedure completion. Details of endovascular devices, including model, specifications, quantity, and usage sequence, as well as type of anesthesia and sedatives (if used), will also be recorded.

Patients included in this trial are recruited from two main pathways: (1) direct referrals from external healthcare facilities and (2) direct admissions to the comprehensive stroke center (Mothership model). This recruitment strategy reflects typical clinical practice and ensures the inclusion of a diverse patient population.

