10.3 Subgroup analyses

Subgroup analyses of the primary endpoint will be conducted based on the following variables:

- (1) Age
- (2) Sex
- (3) Medication history
- (4) Pre-stroke mRS score
- (5) Baseline stroke severity (NIHSS score)
- (6) Blood glucose level at admission
- (7) Baseline infarct size (PC-ASPECTS score and quantitative measurement)
- (8) Baseline collateral circulation status (PC-CS and BATMAN scores)
- (9) Stroke etiology
- (10) Location of basilar artery occlusion
- (11) Time from symptom onset to randomization
- (12) Time from randomization to groin puncture
- (13) Time from randomization to guiding catheter insertion into the vascular puncture sheath
- (14) Time from randomization to cerebrovascular reperfusion

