### 1.5 Sample size

Currently, no large-scale randomized controlled trials (RCTs) exist in this field. Therefore, the calculation of the sample size for this study will be based on the results of the RESCUE-RE registry study conducted in the Chinese population. According to the study, the proportion of patients achieving a mRS score  $\leq 2$  at 90 days post-procedure was 42.03% in the IVT followed by EVT group and 26.14% in the EVT alone group.

Based on the superiority hypothesis, the study aims to determine whether the proportion of patients achieving a modified Rankin Scale (mRS) score of  $\leq 2$  at 90 days is higher in the IVT followed by EVT group compared to the EVT alone group. The statistical hypotheses are defined as follows:

Null Hypothesis  $H_0: p_T - p_C \leq 0$

Alternative Hypothesis  $H_1: p_T - p_C > 0$

$\alpha = 0.025$  (per side),

Assuming a one-sided type I error rate of 0.025 and a statistical power of 80%, with equal allocation between the two groups (1:1), each group will require 136 patients (a total of 272 patients). Considering an anticipated dropout rate of approximately 20%, the final sample size will be adjusted to 340 patients, with 170 patients per group.

Given limited reference data and evidence suggesting the non-inferiority of EVT alone in the anterior circulation, an interim analysis will be conducted after one-third (114) of patients have completed follow-up for the primary endpoint. At this stage, the Data and Safety Monitoring Board (DSMB) will perform a sample size re-estimation based on the efficacy data obtained from both groups.

If the interim analysis the efficacy of the two groups is found to be similar, the study hypothesis will be adjusted to a non-inferiority hypothesis, aiming to verify whether EVT alone is non-inferior to IVT followed by EVT. The specific statistic hypotheses are as follows:

Null Hypothesis  $H_0: p_T - p_C \leq -\Delta$

Alternative Hypothesis  $H_1: p_T - p_C > -\Delta$

$\alpha = 0.025$  (per side),

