#### 2.1.2 Secondary endpoints

The secondary endpoints are as following:

- (1) Proportions of patients with mRS = 0 or 1 at 90 days after stroke onset.
- (2) Proportions of patients with mRS = 0–3 at 90 days after stroke onset.
- (3) mRS score at 90 days after stroke onset.
- (4) NIHSS score at 18–24 hours after procedure, 24–74 hours after procedure, and 5–7 days after stroke onset and their changes from baseline.
- (5) Proportions of patients with a NIHSS score = 0 or 1, a NIHSS score = 0–2, a NIHSS score improvement  $\geq 4$  points, and a NIHSS score improvement  $\geq 8$  points at 18–24 hours after procedure, 24–74 hours after procedure, and 5–7 days after stroke onset.
- (6) Glasgow coma scale score (GCS) at 18–24 hours after procedure, 24–74 hours after procedure, and 5–7 days after stroke onset and their changes from baseline.
- (7) Barthel Index score (BI) and proportions of patients with BI = 95–100 at 30 and 90 days after stroke onset.
- (8) EQ-5D-5L score at 90 days after stroke onset.
- (9) eTICI score and successful reperfusion rates before and after EVT.
- (10) mAOL score and recanalization rates at 24–72 hours after procedure.
- (11) PC-ASPECTS score at 24–72 hours after procedure and 5–7 days after stroke onset.
- (12) Lesion volume based on quantitative imaging detection at 24–72 hours after procedure and 5–7 days after stroke onset.

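### The adjusted analyses of follow-up PC-ASPECTS and lesion volume omit baseline infarct extent, and that of GCS omits baseline GCS, which costs precision on these secondary endpoints

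*SAP*

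**What the plan says.** SAP 3.9.2 compares the continuous secondary endpoints (4, 6, 7, 8, 11 and 12) by t-test or Wilcoxon test, gives mean differences with 95% CIs, and reports unadjusted and adjusted results. It names no model for the adjusted results. The covariates are the same for all of these endpoints: "Covariates include age, pre-stroke mRS, time from onset to randomization, NIHSS score, and collateral circulation".

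Endpoint 11 is "PC-ASPECTS score at 24–72 hours after procedure and 5–7 days after stroke onset", and endpoint 12 is lesion volume at the same two times. Both are follow-up values only. Endpoint 6 (GCS) is specified as follow-up score and as change from baseline.

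On what is known at baseline:

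- Protocol 8.1.4: "Neurological assessments include pre-stroke mRS, NIHSS, and GCS scores". The same section lists PC-ASPECTS among the baseline imaging results.
- The visit schedules (Protocol Appendix 17, SAP 1.8) mark GCS and PC-ASPECTS at baseline. They have no row for lesion volume.
- Protocol 11.2.2 has the independent imaging committee read baseline infarct size as well as follow-up infarct size.
- Protocol 10.3 and SAP 3.9.3 list "Baseline infarct size (PC-ASPECTS score and quantitative measurement") as a subgroup factor for the primary endpoint.

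**The concern.** Of the continuous endpoints that have a baseline value, only NIHSS (endpoint 4) finds its own baseline in the covariate list. The Barthel Index and EQ-5D-5L (7 and 8) are not scheduled at baseline, so nothing is missing there. For PC-ASPECTS and lesion volume, pre-treatment infarct extent enters no specified analysis, although the plan treats it as relevant enough to define a subgroup for the primary endpoint.

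PC-ASPECTS starts at 10 and loses points for each affected region (Protocol Appendix 8). Regions already damaged before randomization will generally still be damaged at follow-up. Part of the spread between patients is therefore not response to treatment, and the listed covariates can remove only some of it.

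Protocol section 2 names infarct size, by PC-ASPECTS and by quantitative imaging, as a secondary objective. At stake are wider intervals than necessary on these endpoints, and no correction if the arms happen to differ in infarct extent at baseline.

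**Working it through.** **1. The plan's own figure.** The only stated sample size is for the primary endpoint. SAP 1.5 assumes "42.03% in the IVT followed by EVT group and 26.14% in the EVT alone group", one-sided alpha 0.025 and 80% power. With the unpooled normal approximation:

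n = (1.960 + 0.842)² × (0.4203 × 0.5797 + 0.2614 × 0.7386) / (0.4203 − 0.2614)² = 7.849 × 0.4367 / 0.02525 = 135.8, so 136 per group.

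Allowing 20% dropout, 136 / 0.8 = 170 per group. Both figures reproduce. They have no bearing on the secondary endpoints except to fix the number of patients: the documents state no SD, effect size or power for PC-ASPECTS, lesion volume or GCS.

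**2. Follow-up score with and without its own baseline.** Let r be the correlation between an endpoint's baseline and follow-up values after allowing for the five listed covariates. It is an assumption, taken here as 0.2 to 0.7.

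- Residual variance with the baseline term, relative to without it: 1 − r².
- Reduction in CI width: 1 − √(1 − r²).
- Equivalent multiple of patients: 1 / (1 − r²).
- Power for a difference that has 80% power without the term (two-sided 0.05): Φ(2.802 / √(1 − r²) − 1.960). That difference is 2.802 × √(2/170) = 0.304 SD at 170 per group, or 0.340 SD at 136.

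| Assumed r | Variance removed | CI narrower by | Equivalent patients | Power (from 80%) |
|---|---|---|---|---|
| 0.2 | 4% | 2.0% | 1.04 × | 81.6% |
| 0.3 | 9% | 4.6% | 1.10 × | 83.6% |
| 0.5 | 25% | 13.4% | 1.33 × | 89.9% |
| 0.7 | 49% | 28.6% | 1.96 × | 97.5% |

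**3. GCS.** The table applies to the raw follow-up score. With equal SDs at baseline and follow-up (assumed), the variance of the change score is 2(1 − r) times that of the raw score. At r = 0.2 or 0.3 this is 1.6 or 1.4, noisier than the raw score; at 0.5 it is 1.0; at 0.7 it is 0.6. With baseline GCS as a covariate the variance is 1 − r², which is (1 − r²) / [2(1 − r)] = (1 + r)/2 of the change-score variance: 0.60, 0.65, 0.75 and 0.85 for the four values of r. The change score does use baseline GCS, but less efficiently than a covariate does.

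**4. Chance imbalance.** At 170 per group the standard error of a baseline difference is √(2/170) = 0.108 SD. If the SD of PC-ASPECTS were 2 points (assumed), one standard error is about 0.2 points. With a follow-up-on-baseline slope of 0.5 to 1.0 (assumed), that shifts the unadjusted follow-up difference by about 0.1 to 0.2 points.

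**5. Missing baselines.** The missing-data rules in SAP 3.2.3 cover the 90-day mRS, incomplete dates and AE relationship, and impute nothing else. Without a further rule, a patient with an unreadable baseline scan would drop out of a model containing that baseline.

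**The case against.** The strongest reply has four parts.

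- **Much of baseline severity is already adjusted for.** NIHSS and collateral status are covariates, and NIHSS items 1a to 1c score consciousness directly. This stands in part. It is why r is defined after those covariates, and why pre-treatment damage cannot be said to remain wholly as noise.
- **The correlation is unknown and may be low.** This stands. Baseline and follow-up imaging may be CT or MRI (Protocol 8.3), and a change of modality would weaken the relation. At r = 0.2 the interval narrows by only 2%. A reader might infer from the last row of the table that the omission wastes nearly half the sample for these endpoints. That needs r = 0.7 after five covariates, and nothing in the documents supports so high a value.
- **Randomization already protects the comparison.** This stands. A reader might infer that a baseline imbalance would produce a false treatment effect. Chance imbalance is covered by the CI and the type I error rate, and it is not systematic bias. Nor should a large imbalance be expected: with an assumed SD of 1.5 to 2, a gap of 0.5 PC-ASPECTS points is about 3.1 to 2.3 standard errors, with a two-sided probability of about 0.002 to 0.02.
- **Baseline lesion volume may not exist.** This stands as a caution. Protocol 11.2.2 and the subgroup list imply a quantitative baseline measurement, but neither Protocol 8.1.4 nor the visit schedule names it.

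One could add that a list introduced by the word include is open-ended. That does not help: no baseline term for these endpoints is pre-specified, and choosing one after the data are seen invites selective reporting.

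**Conclusion.** The point holds for PC-ASPECTS and lesion volume. Their adjusted analyses leave out baseline infarct extent, there is no change score, and at least baseline PC-ASPECTS is collected. For GCS it holds only as a matter of efficiency. A reader might infer that baseline GCS is ignored altogether, but endpoint 6 includes change from baseline.

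The consequence is lost precision and uncorrected chance imbalance on secondary endpoints. For an assumed partial correlation of 0.2 to 0.7, including the baseline would narrow the CI by about 2% to 29%. The documents cannot place the trial within that range. The primary endpoint, its decision rule and the sample size are unaffected. This is an inexpensive improvement worth making before the data are analysed, not a flaw that threatens the trial's conclusion.

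**What to change.** In SAP 3.9.2, specify the adjusted analysis of endpoints 6, 11 and 12 as a linear model (ANCOVA) with the five listed covariates plus:

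- baseline GCS for endpoint 6;
- baseline PC-ASPECTS for endpoints 11 and 12.

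For endpoint 12, use baseline quantitative lesion volume for all patients instead, but only if it is confirmed to be measured at baseline by the same method as at follow-up. Do not use volume for some patients and PC-ASPECTS for others in one covariate, because the two scales run in opposite directions. Consider a transformation of volume.

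Fill a missing baseline value with the pooled mean and add a missing indicator, so that no patient with an outcome is lost. Keep the unadjusted result alongside, as the SAP already requires.

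The cost is a short addition to the SAP, one more model term and a rule for unreadable baseline scans. With baseline GCS and PC-ASPECTS as the added covariates, no new data are needed.

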
Unless otherwise specified, all statistical tests will be two-sided, with a significance level of 0.05 (two-sided). P-values will be reported to three decimal places, and values less than 0.001 will be reported as "P < 0.001".

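### SAP 3.9.2 can pair a rank-test P-value with a mean-difference CI and names no adjusted model; the mismatch matters mainly for lesion volume

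*SAP*

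**What the plan says.** SAP 3.9.2 defines the group opening "For continuous endpoints (4, 6, 7, 8, 11, and 12": NIHSS, GCS, Barthel Index, EQ-5D-5L, PC-ASPECTS and lesion volume. For these, "group comparisons will use independent samples t-tests (if normality and homogeneity of variance are satisfied) or Wilcoxon rank-sum tests (if not". The next sentence has no condition attached: "Mean differences with 95% CIs will also be calculated". Then "Both unadjusted and adjusted results will be reported", with five covariates listed (age, pre-stroke mRS, onset-to-randomisation time, NIHSS, collateral circulation) but no model.

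SAP 3.2.2 sets the level for these tests: "Unless otherwise specified, all statistical tests will be two-sided, with a significance level of 0.05 (two-sided". It also plans descriptive summaries: "Continuous variables will be described using the mean, standard deviation, median, quartiles, minimum, and maximum values". Medians and quartiles therefore appear within each arm, but no between-arm estimate that matches a rank test is named anywhere.

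The 90-day mRS score is treated differently. SAP 3.9.2 gives it one model (ordinal logistic regression) and one effect measure (common odds ratio) with CI, unadjusted and adjusted.

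**The concern.** The test switches with the data and the estimate does not. If normality or equal variance fails, the P-value asks whether values in one arm tend to rank above those in the other, while the CI is for a difference in arithmetic means. With skewed data these are different questions. The report could show P < 0.05 beside a CI that includes 0, or the reverse.

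A rank-sum test cannot take the five covariates, so the adjusted result must come from a model that the SAP does not name. Nor does the SAP name the normality test, its threshold, or whether it is applied per arm, so even the choice of branch is not fully fixed in advance.

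At stake are the clarity of the secondary results and, for lesion volume, a good part of the information in the data.

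**Working it through.** **Sample size, used only to set n.** SAP 1.5 gives "42.03% in the IVT followed by EVT group and 26.14% in the EVT alone group", one-sided 0.025 and 80% power. With the unpooled formula:

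n = (1.960 + 0.842)² × (0.4203 × 0.5797 + 0.2614 × 0.7386) / (0.4203 − 0.2614)² = 135.8, so 136 per group. Then 136 / 0.80 = 170.

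Both figures match the plan. The simulations use 136, 150 or 170 per arm.

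**Lesion volume.** The documents give no distribution, SD or expected effect, so these are assumptions: log-normal volumes, 150 scans per arm, 3,000 trials per setting. Each trial compares the two-sided Wilcoxon result (P < 0.05) with whether the 95% CI for the mean difference excludes 0.

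| log-SD | true ratio | Wilcoxon significant | mean-difference CI excludes 0 | t-test on log volume significant | Wilcoxon and mean CI disagree |
|---|---|---|---|---|---|
| 1.0 | 0.70 | 84.5% | 67.3% | 86.6% | 23.1% |
| 1.0 | 0.65 | 95.6% | 82.4% | 96.2% | 15.1% |
| 1.3 | 0.70 | 63.9% | 37.3% | 66.1% | 36.1% |
| 1.3 | 0.65 | 80.5% | 51.6% | 82.5% | 35.3% |
| 1.6 | 0.70 | 47.2% | 19.9% | 48.7% | 35.4% |
| 1.6 | 0.65 | 62.2% | 28.2% | 64.9% | 42.2% |

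**Hand check of the 1.3 / 0.70 row.**
- Log scale: z = (|ln 0.70| / 1.3) × √(150/2) = 0.274 × 8.66 = 2.38. Power = Φ(2.38 − 1.96) = 66%.
- Wilcoxon, with relative efficiency 3/π = 0.955: z = 2.38 × √0.955 = 2.32. Power = 64%.
- Mean difference, with the larger mean set to 1: squared coefficient of variation = e^1.69 − 1 = 4.42. SE = √(4.42 × (1 + 0.70²) / 150) = 0.210. z = 0.30 / 0.210 = 1.43, and power is about 30%. The simulated 37% is higher because the normal approximation is rough with this much skew.
- Direction: the net gap is 63.9 − 37.3 = 26.6 points and total disagreement is 36.1. So (36.1 + 26.6) / 2 = 31% of trials have a significant Wilcoxon test with a CI that includes 0, and about 5% the reverse.

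**Second simulation** (2,500 trials per setting, 136 and 170 per arm, shift of 0.30 SD on the log scale). Disagreement:
- log-SD 0.5: 12.1% to 12.8%
- log-SD 1.0: 26.3% to 26.6%
- log-SD 1.5: 40.0% to 43.4%
- no true effect: 3.6% to 6.5%

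**Bounded scores** (same simulation, assumed shapes):
- NIHSS-like with an effect: 7.8% to 8.3%
- Barthel-like with an effect: 6.6% to 7.4%
- crossing effects: 3.4% to 7.1%
- no effect: 1.8% to 1.9%

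A further check at 150 per arm with a common odds ratio of 1.6 gave 5.7% to 7.8% for PC-ASPECTS-, GCS-, Barthel- and NIHSS-like scores. One other NIHSS-like shape gave 13%. EQ-5D-5L was not simulated separately.

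**The case against.** Choosing between a t-test and a Wilcoxon test by a normality check is a conventional, prespecified rule. SAP 3.9.2 assigns the group comparison to the test and says mean differences are also calculated, so they can be read as supplementary. These are secondary endpoints with no stated decision rule. Most of this stands, and it is why the point is minor. It does not supply an estimate to go with the Wilcoxon P-value, nor a model for the adjusted analysis.

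A reader might infer more than the documents support:

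- **That P-value and CI will often disagree on all these endpoints.** They will not. For the bounded scores the rate is what two valid tests near a threshold produce. High rates need strong right skew and a real effect, and lesion volume is the plausible candidate.
- **That the mean-difference CI is invalid, or that the check rejects the mean.** The check concerns the t-test's assumptions, not the mean as a target. At these sample sizes the interval is valid for its own target in most of the settings tried.
- **That the adjusted result must have a third target.** The SAP does not say. An adjusted mean difference from a linear model would share the unadjusted one's target. The gap is that no model is named.

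Log-normal data also favour the log-scale model by construction, so its advantage in the table depends on that assumption.

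**Conclusion.** The mismatch is in the text and does not depend on simulation: when the check fails, SAP 3.9.2 takes the P-value from ranks and the CI from means, and leaves the adjusted model open. Its practical size depends on the endpoint. For lesion volume with a real effect, disagreement on significance is about 15% to 42%, mostly a significant test beside a CI that includes 0. That range rests on log-normal volumes with log-SD 1.0 to 1.6, ratio 0.65 to 0.70 and 150 per arm. With mild skew (log-SD 0.5) it is 12% to 13%, and with no effect about 4% to 7%. For the bounded scores it is about 2% to 8% in most assumed settings.

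The primary conclusion rests on the adjusted risk difference (SAP 3.9.1), and the mRS shift analysis has its own model, so neither is touched. The sample size does not change. This is a low-severity improvement in wording.

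**What to change.** In SAP 3.9.2, drop the normality and variance pre-test. Name one model per endpoint that supplies the P-value, effect, 95% CI and adjusted result.

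- **Lesion volume:** linear model on log(volume + 1), with the unit stated (for example mL), because adding 1 makes the result depend on the unit. Report an approximate ratio with 95% CI, unadjusted and adjusted for the five listed covariates.
- **NIHSS, GCS, Barthel, EQ-5D-5L, PC-ASPECTS:** either ordinal logistic regression with a common odds ratio, unadjusted and adjusted, as the SAP already does for the mRS, or a linear model with robust standard errors for the mean difference. State which one for each endpoint, including the changes from baseline in NIHSS and GCS.

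Do not add a Hodges-Lehmann shift for the scores. Heavy ties often make its CI include 0 when the Wilcoxon test is significant. On assumed tied, bounded scores the two disagreed in 23% to 61% of simulated trials, and in one check the estimate was exactly 0 in 80% (GCS-like) and 89% (Barthel-like).

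The cost is SAP wording, best settled before unblinding. Ratios and odds ratios are slightly less familiar to readers; mean differences and medians can stay as description.
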